8.3 Study period

The study period was from 01/01/2000 to 31/12/2023 (when the study end date was not reached in a data source, the study end for that source was the last date of available data) (see **Table 3** for more details).

8.4 Follow-up

Study participants will be followed up from the date of first exposure to Azathioprine until date of:

1) censoring or loss to follow-up, 2) end of data availability, or 3) the end date of exposure (whichever occurs first).

	D2.2.3 - Study Protocol for P3-C1-014	
	Author(s): [name], [name]	Version: V4.0
	Dissemination level: Public	

Table 4. Operational definition of time 0 (index date) and other primary time anchors.

Study population name(s)	Time Anchor Description (e.g. time 0)	Number of entries	Type of entry	Washout window	Care Setting ¹	Code Type ²	Diagnosis position	Incident with respect to...	Measurement characteristics/ validation	Source of algorithm
Individuals initiating treatment with Azathioprine (objective 1,2, 3 and 4)	Date of first treatment with Azathioprine during study period	Single entry	Incident	Any time prior to study entry date	OP	RxNorm	N/A	Exposure	N/A	N/A

¹ IP = inpatient, OP = outpatient, ED = emergency department, OT = other, n/a = not applicable

	D2.2.3 - Study Protocol for P3-C1-014	
	Author(s): [name], [name]	Version: V4.0
		Dissemination level: Public

8.5 Study population with inclusion and exclusion criteria

The study population will include all individuals observed in one of the participating data sources during the study period (1st January 2000 to 31st December 2023) and having at least 1 year of database history.

Patients will be excluded if the start date in the database falls within 365 days prior to the index date, as sufficient data availability is required.

The operational definitions of the inclusion and exclusion criteria are presented by means of **Table 5** and **Table 6** , respectively.

	D2.2.3 - Study Protocol for P3-C1-014	
	Author(s): [name], [name]	Version: V4.0
	Dissemination level: Public	

Table 5. Operational definitions of inclusion criteria.

Criterion	Details	Order of application	Assessment window	Care Settings ¹	Code Type	Diagnosis position ²	Applied to study populations:
Prior database history	Study participants will be required to have 365 days of prior history observed before the index date	Prior	[-365,-1]	OP	N/A	N/A	All individuals within selected databases
Observation period in the database during the period	All individuals present in the 2000-2023 (or the latest date available)	after	N/A	OP	N/A	N/A	All individuals within selected databases
User of Azathioprine (exposure)	Prescription record of azathioprine	after	Study period	OP	RxNorm	N/A	All individuals within selected databases

¹ IP = inpatient, OP = outpatient, ED = emergency department, OT = other, n/a = not applicable

² Specify whether a diagnosis code is required to be in the primary position (main reason for encounter)

	D2.2.3 - Study Protocol for P3-C1-014	
	Author(s): [name], [name]	Version: V4.0
	Dissemination level: Public	

Table 6. Operational definitions of exclusion criteria.

Criterion	Details	Order of application	Assessment window	Care Settings ¹	Code Type	Diagnosis position ²	Applied to study populations:	Measurement characteristics/validation	Source for algorithm
N/A	N/A	N/A	N/A	N/A	N/A	N/A	N/A	N/A	N/A

¹ IP = inpatient, OP = outpatient, ED = emergency department, OT = other, n/a = not applicable

² Specify whether a diagnosis code is required to be in the primary position (main reason for encounter)

	D2.2.3 - Study Protocol for P3-C1-014	
	Author(s): [name], [name]	Version: V4.0
		Dissemination level: Public

8.6 Variables

Preliminary concept/code lists used for the identification of exposure/s and/or outcomes are included as Supplementary Documents in **Appendix I**. These will be refined during the study execution following the DARWIN EU® Phenotyping standard processes, which involve the review of code lists by clinical experts, and the review of phenotypes after their execution in the participating databases. The concepts sets already contain more broad concepts because the some of the indications have quite low granularity.

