11. LIMITATIONS OF THE RESEARCH METHODS

Regarding azathioprine use, the recording of the prescription of the drug (e.g. concept id at clinical drug level or at ingredient level), and the prescriptions themselves may vary across databases. In addition, a recording of a prescription or dispensation does not mean that the patient actually took the drug. In addition, assumptions around the duration of drug use will be unavoidable and might lead to overestimating treatment duration of treatment (considering a 30-day drug gap era).

	D2.2.3 - Study Protocol for P3-C1-014	
	Author(s): [name], [name]	Version: V4.0
		Dissemination level: Public

For this study, the indication of use is important and predefined indications of use have been identified. Not all of these indications of interest might be present within the database (i.e. in DP with less granular source coding such as IPCI). For that reason, it might be interesting to use more broad definitions of the indication of use (e.g. look for “inflammatory disease of liver” and not necessarily “autoimmune hepatitis”. These broad searches might impose a potential of misclassification however, as we search in a relatively small window, 3 months before and 1 month after, around the index date (first prescription of azathioprine during study period) this risk of misclassification is probably minimal. Also, the large-scale characterisation (looking for top 10 disease codes) might provide insight into the indication of use on top of the indications which have been predefined.

The study period is from 2000 until 2023 however not all DPs have that long observation time. For IPCI, observation period starts from 2008 and for SIDIAP from 2005.

Small cell counts may affect the analysis for some subgroup strata. If the numbers are too low, counts will not be disclosed for governance reasons.

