APPENDIX I:

Table S1. Code list for drug of interest .

Concept set name	IDs (including descendants)
Azathioprine	19014878

Table S2. Code list for indication definitions.

Concept set name	Included concepts	IDs (including descendants)
Organ transplantation	Transplantation Transplant follow-up Disorder related to transplantation	4300185 4081759 4179244
Severe rheumatoid arthritis or chronic polyarthritis	Rheumatoid arthritis Chronic polyarthritis	80809 3168431
Inflammatory bowel diseases	Inflammatory bowel disease Ulcerative colitis Crohn's disease	4074815 81893 201606
Autoimmune hepatitis	Autoimmune hepatitis	200762
Systemic lupus erythematosus	Systemic lupus erythematosus Cutaneous lupus erythematosus	257628 4324123
Dermatomyositis	Dermatomyositis	80182
Polyarteritis nodosa	Polyarteritis nodosa	320749
Pemphigus vulgaris and bullous pemphigoid	Pemphigus Bullous pemphigoid	135338 4298692
Behcet's disease	Behcet's syndrome	436642
Refractory autoimmune haemolytic anaemia	Hemolytic anemia	435503
Refractory idiopathic thrombocytopenic purpura	Immune thrombocytopenia Thrombocytopenic purpura	4103532 4119134
Polymyositis	Polymyositis	80800
Pyoderma gangrenosum	Pyoderma gangrenosum	133283
Multiple sclerosis	Multiple sclerosis	374919
Myasthenia gravis	Myasthenia gravis	76685

	D2.2.3 - Study Protocol for P3-C1-014	
	Author(s): [name], [name]	Version: V4.0
	Dissemination level: Public	

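### Six of the 15 indication rows in Table S2 use codes wider than their labels, and nothing in the protocol measures 'severe' or 'refractory'

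*Protocol*

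**What the plan says.** Objective 2 (protocol section 7) asks for the percentage of azathioprine users in each approved indication on a fixed list. Objectives 1, 3 and 4 report age and sex, prior drugs and conditions, and treatment duration overall and by the same list. Three labels carry a qualifier of severity or treatment resistance: severe rheumatoid arthritis, refractory autoimmune haemolytic anaemia and refractory idiopathic thrombocytopenic purpura.

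Section 8.6.3 assigns an indication when a disease code is present from 90 days before to 30 days after the index date. It gives no rule on prior treatment, severity or laboratory values.

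The codes are in Appendix I, Table S2, each taken with its descendants and with no exclusions listed. The haemolytic anaemia row has the single concept "Hemolytic anemia". The thrombocytopenic purpura row has "Immune thrombocytopenia Thrombocytopenic purpura". The rheumatoid arthritis row has "Rheumatoid arthritis Chronic polyarthritis". The systemic lupus row adds "Cutaneous lupus erythematosus".

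Section 8.6 calls the lists preliminary and states: "The concepts sets already contain more broad concepts because the some of the indications have quite low granularity". Section 11 says that, for sources with less granular coding, "it might be interesting to use more broad definitions of the indication of use". Its example is a general inflammatory liver disease code in place of autoimmune hepatitis. It then judges the resulting misclassification to be probably minimal because the window around the index date is short.

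**The concern.** The labels and the codes describe different patient groups, and the labels are what will appear in the report. The study is meant to give the regulator context for a liver-related signal, and the main content of that context is who receives azathioprine, for what, and for how long. A percentage, age distribution or duration printed under refractory autoimmune haemolytic anaemia would describe anyone with a haemolytic anaemia code near the first prescription. The same holds, to differing degrees, for five other rows.

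The residual category is affected too. A patient caught only by an over-wide row is counted inside an approved indication and leaves the none-of-the-above group, so apparent use outside the listed indications falls.

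Section 11 would reassure a reader on this point, but for a reason that does not apply to it.

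**Working it through.** No sample size, power or event figure bears on this, so the check sets labels against codes and then looks for any rule elsewhere that closes the gap.

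**Step 1: rows wider than their labels (Table S2).**

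| Row label | Concepts listed | What is lost |
|---|---|---|
| Severe rheumatoid arthritis or chronic polyarthritis | Rheumatoid arthritis; chronic polyarthritis | severe |
| Refractory autoimmune haemolytic anaemia | Haemolytic anaemia | refractory; autoimmune |
| Refractory idiopathic thrombocytopenic purpura | Immune thrombocytopenia; thrombocytopenic purpura | refractory; idiopathic, through the second concept |
| Systemic lupus erythematosus | Systemic lupus; cutaneous lupus | systemic, through the second concept |
| Pemphigus vulgaris and bullous pemphigoid | Pemphigus; bullous pemphigoid | vulgaris |
| Organ transplantation | Transplantation; transplant follow-up; transplant-related disorder | organ |

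**Step 2: count.** Rows with a severe or refractory qualifier: 3, of which 3 lack it in their codes. Further rows with a concept wider than the label: 3. Total 3 + 3 = 6 of 15. The remaining 15 − 6 = 9 rows match by concept name: inflammatory bowel disease, autoimmune hepatitis, dermatomyositis, polyarteritis nodosa, Behçet's disease, polymyositis, pyoderma gangrenosum, multiple sclerosis and myasthenia gravis.

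**Step 3: is the qualifier restored elsewhere?** Section 8.6.3 uses disease codes only. Tables 7 and 9 repeat the window and the vocabulary and add nothing. Sections 8.6 and 10 describe a review of code lists and phenotypes. That review can narrow a concept, but neither section adds a criterion for severity or refractoriness, or a change of label. Section 8.8.4 keeps the prespecified indications as the rows of Output Tables 3 and 8.

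**Step 4: does the short window answer it?** A window of −90 to +30 days limits error of timing: it makes it more likely that the coded disease was current when treatment began. It says nothing about what kind of disease the code denotes. A general haemolytic anaemia code recorded the day before the first prescription is still not specific to autoimmune or refractory disease. The reason given in section 11 therefore does not support its conclusion for these six rows.

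**Step 5: section 11 against Table S2.** Section 11's only example of broadening concerns autoimmune hepatitis. Table S2 lists only the specific concept for that row, while six other rows are broadened without being named in section 11. Section 11 also speaks of broadening as something that might be done, whereas section 8.6 says it has already been done.

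**Step 6: size.** The protocol gives expected azathioprine users per database but no counts per indication or per code. The share of patients in any row who do not meet its label cannot be computed.

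**The case against.** The breadth is deliberate and partly disclosed. Section 8.6 says the sets are preliminary and already broad. Section 10 provides for review by two clinical epidemiologists and for diagnostics that inform whether multiple definitions are needed. Section 11 admits that broad searches may misclassify. Everyone counted has started azathioprine close to the code, which plausibly enriches the rows for more serious disease. The large-scale characterisation per indication would let readers see some of what a broad row contains, and objective 2 speaks of potential indications.

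Much of this stands as mitigation. Nothing is concealed, and the review makes the repair easy. It does not remove the problem: the disclosure names no row, no planned step defines or drops the two qualifiers, objective 2 also calls the indications approved, and the protocol neither argues nor checks the enrichment.

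Four stronger readings are tempting, and the document does not support them:

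- A reader might infer that Table S2 as a whole fails to identify its diseases. Nine of 15 rows match by name. In the rheumatoid arthritis row the disease is identified and only severity is lost, and the thrombocytopenic purpura row does include the immune form.
- A reader might infer that autoimmune hepatitis will be undercounted in coarsely coded sources. That depends on whether their vocabularies have a code for it, which the protocol does not say.
- A reader might infer that all sources were given broad sets because of IPCI. Section 8.6 attributes the breadth to the indications. IPCI appears only in section 11, as an example of a less granular source.
- A reader might hold the transplant row to solid organs. The protocol's own label says organ, so the mismatch is only that the concept carries no organ limit.

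**Conclusion.** The point holds as a mismatch between labels and codes in six of 15 rows, including all three rows with a severe or refractory qualifier. It touches every objective, because all four are reported per indication. It should be corrected before the results are tabulated.

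The conclusion rests on the concept names printed in Table S2, taken with descendants and without exclusions, and on code presence being the only assignment rule. If the code review later narrows a concept, that row's breadth is resolved, but the severe and refractory labels remain unmeasured unless a rule is added or the labels change. The number of patients affected, and whether the autoimmune hepatitis row is undercounted anywhere, cannot be determined from the document.

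**What to change.** 1. Drop 'severe' and 'refractory' from the output labels and name each row for what its codes capture, for example haemolytic anaemia; immune thrombocytopenia or thrombocytopenic purpura; rheumatoid arthritis of any severity or chronic polyarthritis; systemic or cutaneous lupus; pemphigus or bullous pemphigoid; transplantation.
2. Where a specific concept exists, report the narrow set as its own row beside the broad one in Output Tables 3 and 8. Table S2 already lists immune thrombocytopenia and systemic lupus separately. Concepts for autoimmune haemolytic anaemia and pemphigus vulgaris should be confirmed in the planned code review.
3. In section 11, list the six affected rows and remove the statement that the short window makes this misclassification minimal.
4. Reconcile section 11's liver example with Table S2: either add the broad liver concept as a separate, labelled row or replace the example with a broadening that is actually used.

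The cost is code-list edits, which the phenotype review already foresees, a few extra table rows and a short rewrite of section 11. Some narrow rows may be small and fall under the suppression of cell counts below 5.

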8.6.1 Exposure/s

Azathioprine exposure consists of a prescription record of azathioprine (for systemic use thus oral or parenteral use). The operational definition of exposure is described by means of **Table 7**.

	D2.2.3 - Study Protocol for P3-C1-014	
	Author(s): [name], [name]	Version: V4.0
	Dissemination level: Public	

Table 7. Operational definitions of exposure.

Exposure group name(s)	Details	Washout window	Assessment Window	Care Setting ¹	Code Type	Diagnosis position ²	Applied to study populations	Incident with respect to...	Measurement characteristic s/ validation	Source of algorithm
Azathioprine	Preliminary code lists provided in Appendix I	[-inf,-1], for incident use only	Anytime post start of the study date	OP	RxNorm	N/A	All eligible individuals in the database	Azathioprine use	N/A	N/A
Azathioprine + indication of use	Preliminary code lists provided in Appendix I	n/a = not applicable	Indication of use in - 90/+30 days of index date	OP	SNOMED codes to assess indication of use	Yes (indication of use)	All incident users of azathioprine	Azathioprine use	N/A	N/A

¹ IP = inpatient, OP = outpatient, ED = emergency department, OT = other, n/a = not applicable

² Specify whether a diagnosis code is required to be in the primary position (main reason for encounter)

	D2.2.3 - Study Protocol for P3-C1-014	
	Author(s): [name], [name]	Version: V4.0
	Dissemination level: Public	

8.6.2 Outcome/s

The study outcome(s) are described conceptually, and the context or rationale for the choices are provided in this section. The operational definition of the outcomes is presented in the [Table 8](#).

Table 8. Operational definitions of outcome.

Outcome name	Details	Primary outcome ?	Type of outcome	Washout window	Care Settings ¹	Code Type	Diagnosis Position ²	Applied to study populations	Measurement characteristics/validation	Source of algorithm
N/A	N/A	N/A	N/A	N/A	N/A	N/A	N/A	N/A	N/A	N/A

¹IP = inpatient, OP = outpatient, ED = emergency department, OT = other, n/a = not applicable

²Specify whether a diagnosis code is required to be in the primary position (main reason for encounter)

8.6.3 Other covariates, including confounders, effect modifiers and other variables

The study covariates are described conceptually, and the context or rationale for the choices are provided in this section. The operational definition of the covariates is described in the [Table 9](#).

Covariates for the patient-level characterisation

To characterise the new initiators of Azathioprine, the covariates will include:

- age at the index date (first prescription of Azathioprine) presented as a mean/median age as well as proportion of patient stratified within age groups (<18, 18-44, 45-64, 65-79, and >=80), overall and per indication
- sex (male/ female), overall and per indication.
- Conditions considered indications for Azathioprine use, will be assessed within -90/+30 days of the index date. These indications will be identified based on the presence of disease codes. The preliminary code list for each condition of interest is available in [Appendix I](#).

Indications:

- Organ transplantation
- Severe rheumatoid arthritis or chronic polyarthritis
- Inflammatory bowel diseases
- Autoimmune hepatitis
- Systemic lupus erythematosus
- Dermatomyositis
- Polyarteritis nodosa
- Pemphigus vulgaris and bullous pemphigoid
- Behcet's disease
- Refractory autoimmune haemolytic anaemia
- Refractory idiopathic thrombocytopenic purpura
- Polymyositis

	D2.2.3 - Study Protocol for P3-C1-014	
	Author(s): [name], [name]	Version: V4.0
		Dissemination level: Public

- Pyoderma gangrenosum
 - Multiple sclerosis
 - Myasthenia gravis
 - None of the above/missing
- Large-scale characterisation: overall and per indication of drugs (by RxNorm code at ingredient level) and conditions (by standard SNOMED code) within one year prior to the index date (-365 to -1 day to the index date) and at the index date will be assessed. While all conditions and medications above 1% will be available within the Shiny App, only the 10 most frequent conditions and drugs will be described within the report. Drugs will be reported by ingredient and not by strength or formulation
 - Treatment duration overall and per indication, will be assessed from the index date until date of: 1) censoring or loss to follow-up, 2) end of data availability, or 3) the end date of exposure (whichever occurs first). Furthermore, to provide more context, also the proportion (%) of patients with a duration that fall within a prespecified treatment duration group will be calculated and provided, both for the overall treatment duration as per indication. The prespecified treatment duration groups will be: <12 months, 12-24 months, 2-3 years, 3-4 years, 4-5 years, 5-10 years and ≥10 years.

	D2.2.3 - Study Protocol for P3-C1-014	
	Author(s): [name], [name]	Version: V4.0
	Dissemination level: Public	

Table 9. Operational definitions of covariates.

Characteristic	Details	Type of variable	Assessment window	Care Settings ¹	Code Type	Diagnosis Position ²	Applied to study populations	Measurement characteristics / validation	Source for algorithm
Demographics	Age and sex at index date	Numeric, continuous, binary	All history	OP	N/A	N/A	Incident azathioprine users	N/A	N/A
Indications	Prespecified indications of interest - 90/+30 days of the index date	Count, binary	[-90, +30]	OP	SNOMED	N/A	Incident azathioprine users	N/A	N/A
Medication use, comorbidities	All history prior to the index date (large-scale characterisation)	Count, binary	[-365, -1] and [0,0]	OP	SNOMED, RxNorm	N/A	Incident Azathioprine users	N/A	N/A
Treatment duration	Duration of treatment with Azathioprine for the: 
 - new users of azathioprine use - New users of azathioprine per indication 	Numeric, continuous	[0, end of exposure]	OP	N/A	N/A	Incident azathioprine users	N/A	N/A

¹ IP = inpatient, OP = outpatient, ED = emergency department, OT = other, n/a = not applicable

² Specify whether a diagnosis code is required to be in the primary position (main reason for encounter)

	D2.2.3 - Study Protocol for P3-C1-014	
	Author(s): [name], [name]	Version: V4.0
		Dissemination level: Public

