6. RATIONALE AND BACKGROUND

Azathioprine is a purine analogue and prodrug of mercaptopurine that is used as an immunosuppressive medication alone or in combination with other immunosuppressive therapy to prevent rejection following organ transplantation and to treat certain autoimmune diseases, where it is considered a steroid-sparing agent. Examples of autoimmune diseases that could be treated with azathioprine are rheumatoid arthritis, inflammatory bowel disease, systemic lupus erythematosus (SLE), polymyositis, dermatomyositis, multiple sclerosis (MS) and myasthenia gravis(1-7).

Azathioprine is associated with minor usually transient and asymptomatic elevations of aminotransferase levels and with rare instances of acute cholestatic liver injury and with long-term use, portal hypertension may occur(8, 9).

A signal procedure regarding a potential association between azathioprine and non-cirrhotic portal hypertension/portosinusoidal vascular disease (PSVD) - which is a rare disorder characterised by signs of portal hypertension in the absence of an identifiable aetiology, such as cirrhosis - is needed. A liver biopsy is mandatory for the diagnosis of PSVD.(10) Specific histologic signs include obliterative portal venopathy, nodular regenerative hyperplasia and incomplete septal fibrosis (10).

This study is intended to support the signal evaluation by providing information about the use of azathioprine, including the most frequent indications, the age- and sex distribution at initiation of treatment, and the treatment duration for all indications combined, and for each indication separately.

	D2.2.3 - Study Protocol for P3-C1-014	
	Author(s): [name], [name]	Version: V4.0
	Dissemination level: Public	

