8.7 Study size

No sample size has been calculated as this is a descriptive Drug Utilisation Study where we are interested in the characteristics of all incident cases of new users of Azathioprine in each database. Based on a preliminary feasibility assessment, the expected person counts for Azathioprine were 900 for IMASIS, 6,000 for IPCI, 23,700 for IQVIA DA Germany, 24,500 for SIDIAP and 52,100 for CPRD GOLD.

The study period is from 2000-2023 but it should be noted that not all DPs do have observations period starting from 2000 on. For IPCI, observation period starts from 2008 and for SIDIAP from 2005.

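### The -90/+30-day indication window lets a code first recorded after azathioprine starts count as the reason for treatment, and section 11's reassurance does not cover codes the drug itself may cause

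*Protocol*

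**What the plan says.** The protocol gives the same window in Table 7 (section 8.6.1), section 8.6.3 and Table 9: "Conditions considered indications for Azathioprine use, will be assessed within -90/+30 days of the index date". The assignment rule follows directly: "These indications will be identified based on the presence of disease codes". No passage treats a code recorded before the first prescription differently from one that first appears afterwards.

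On the liver, section 6 states: "Azathioprine is associated with minor usually transient and asymptomatic elevations of aminotransferase levels and with rare instances of acute cholestatic liver injury". It gives no frequency and no time to onset. Appendix I, Table S2, defines autoimmune hepatitis by a single concept, 200762, with descendants. Section 8.6 says of the code lists: "These will be refined during the study execution following the DARWIN EU® Phenotyping standard processes".

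Section 11 remarks that, for sources with coarse coding such as IPCI, "it might be interesting to use more broad definitions of the indication of use". Its example is a general liver-inflammation concept in place of autoimmune hepatitis. It concedes that broad searches can misclassify, but holds that "this risk of misclassification is probably minimal" because the window is short, and it counts the month after the index date as part of that short window.

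**The concern.** An indication should precede, or at least coincide with, the decision to prescribe. For most of the 15 named indications, a code in the month after the start is plausibly late recording of a known diagnosis. For a liver indication there is a second explanation: the code may record something the drug did. The rule cannot tell the two apart.

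Section 6 sets out the purpose: "This study is intended to support the signal evaluation by providing information about the use of azathioprine, including the most frequent indications". The signal is hepatic. If a liver reaction is filed as autoimmune hepatitis, that row's share is too high. Its age, sex and duration summaries then include people treated for something else. Duration is that of the first treatment era (section 8.8.1), so anyone who stopped soon after such a reaction would pull the row's duration down. A patient could even be placed in the row by a code recorded after that era had ended.

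**Working it through.** There is no planned figure to reproduce, so the check is a reading of the sections against each other, followed by a range under stated assumptions.

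**1. The window.** It has 90 + 1 + 30 = 121 days, of which 30 (30/121 = 24.8%) follow the index date. This describes the window only. Diagnoses are not spread evenly around a first prescription, so it is not the share of codes that fall after the start.

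**2. What can enter the autoimmune hepatitis row now.** Under Table S2, a liver event qualifies only if it is coded as autoimmune hepatitis or a descendant of that concept. A raised aminotransferase value does not qualify. The present opening is narrow.

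**3. What could enter after broadening.** With a general liver-inflammation concept, any liver-inflammation code on days +1 to +30 would qualify. Section 8.6 keeps the lists open and says some concept sets are already broad. Table S2 bears this out: refractory autoimmune haemolytic anaemia is defined by haemolytic anaemia in general.

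**4. Section 11's argument.** A short window limits chance overlap with unrelated disease. It does not limit codes that treatment causes, because those can arise only after treatment starts, and the month after the index date is where an early reaction would be recorded. The argument is sound for coincidence and silent on reverse attribution.

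**5. Whether any output would show it.** Section 11 looks to the large-scale characterisation for further insight into indications. That covers [-365, -1] and [0, 0] (section 8.6.3, Table 9, section 8.8.4), so days +1 to +30 are not in it. None of the output tables in section 8.8.4 splits indications by when the code was recorded.

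**6. Size under assumptions.** Let t be the share of initiators truly treated for autoimmune hepatitis, and r the share of the others who receive a qualifying liver code on days +1 to +30. The documents give neither.

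False share of the row = (1 − t)r / [t + (1 − t)r]

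The last column uses the section 8.7 count of 6,000 for IPCI, from "900 for IMASIS, 6,000 for IPCI, 23,700 for IQVIA DA Germany, 24,500 for SIDIAP and 52,100 for CPRD GOLD".

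| t (assumed) | r (assumed) | False share | IPCI: false / true |
|---|---|---|---|
| 5% | 0.05% | 0.000475/0.050475 = 0.9% | 2.9 / 300 |
| 3% | 0.1% | 0.00097/0.03097 = 3.1% | 5.8 / 180 |
| 3% | 0.5% | 0.00485/0.03485 = 13.9% | 29.1 / 180 |
| 3% | 1% | 0.0097/0.0397 = 24.4% | 58.2 / 180 |
| 1% | 2% | 0.0198/0.0298 = 66.4% | 118.8 / 60 |

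The low values of r suit the present narrow concept; the high ones could arise only with a broad one. A range from 0.9% to 66% reflects the inputs alone. It shows that the size cannot be fixed from the protocol.

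**7. With the window ended at day 0.** Codes first recorded on days +1 to +30 contribute nothing to any row. How many true, late-coded cases are lost cannot be computed from the document, but reporting both windows would show it.

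**The case against.** The strongest reply is that the harm depends on a definition the protocol has not adopted. Other concept sets were made broad, but autoimmune hepatitis was left narrow, and section 11 only calls broader definitions potentially interesting. A reader might infer that section 11 replaces the autoimmune hepatitis definition; it does not. Section 6 calls the aminotransferase changes minor and usually transient and the cholestatic injury rare, and it mentions neither drug-induced hepatitis nor early onset. This stands, and it is why the present exposure is judged probably small.

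A reader might also infer that the reaction under assessment would itself be reported as an indication. The documents do not support that. The signal concerns non-cirrhotic portal hypertension and porto-sinusoidal vascular disease. Section 6 mentions portal hypertension with long-term use and says a biopsy is mandatory for diagnosing the vascular disease. An early liver code is a different event.

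A +30-day allowance has a plausible purpose, catching late-recorded diagnoses, although the protocol does not state it. Shortening the window for one row only would make the rows non-comparable. This also stands, so the main window should remain common to all indications. If the liver concept were widened, unrelated liver codes on days -90 to 0 would still be accepted, so ending the window at day 0 cures only part of that weakness.

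Finally, code lists and phenotypes undergo clinical review and a CohortDiagnostics run (sections 8.6 and 10), and checklist item 12.1 points to section 11 for a discussion of bias. That review concerns which codes are used. Nothing in the protocol says it examines whether a code came before or after the first prescription.

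**Conclusion.** The point holds as a gap in the indication rule and an incomplete argument in section 11. Codes first recorded after the start count as indications, nothing separates late coding from a drug effect, and no listed output would reveal the difference. Under the current autoimmune hepatitis concept the effect is probably small; it would grow if the concept were widened.

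No numerical size can be claimed. A reader might take one of the illustrative rows above as an estimate of false autoimmune hepatitis cases, but both inputs are assumptions and the documents offer nothing to anchor them. The effect on duration is likewise conditional: it requires that patients with an early liver reaction stop early, which the protocol does not say.

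**What to change.** - Keep [-90, +30] as the main window for all indications, so that the rows stay comparable.
- In output Table 3 (indication shares) and Table 8 (duration), report the same results with the window ended at the index date, [-90, 0]. For every indication, give the number of patients assigned only by a code on days +1 to +30. Read that number as a ceiling on reverse attribution, since it also includes late coding and patients whose earlier code lies before day -90.
- If the autoimmune hepatitis concept is broadened in any database, accept the broadened codes only up to day 0.
- Amend the section 11 sentence to say that the short window limits chance coincidence but does not protect against codes that treatment may cause, and refer to the [-90, 0] results.

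**Cost.** One extra run and one extra column. In the [-90, 0] version some late-coded true cases move to the None of the above/missing row. Section 8.8 suppresses counts below 5. The new number is the difference between two reported counts, so where it is small one of those counts may need masking as well.
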